Step 1: Baseline Assessment. Participants who sign informed consent will be asked to complete a Baseline Assessment via Qualtrics. Participants will be sent a secure link to the Qualtrics survey via text or email. The Baseline will take approximately 30 minutes to complete and will include questions about demographics, parenting, mental health, stress and coping, motivation, and drinking and other substance use.

[figure not shown]
Step 2: Catalyst Training. Following completion of the Baseline, participants will participate in a one-on-one 15-minute training session with the RA via Zoom to provide training on how to download and use the Catalyst app. In order to avoid fraudulent participants, participants will be asked to turn on their camera for 1 minute of the training, after which they will be allowed to turn off their cameras for the remainder of the training if that makes them more comfortable. Participants who complete both the baseline survey and the Catalyst training session will receive a \$25 Amazon gift card upon completion of the Catalyst training session.

Step 3: 28-day MRT. After completing the training, the TMI sequence of EMAs and TMI text messages will begin as described below and will last for 28 days.

TMI Sequence and Randomization

Upon completion of the Catalyst training, the TMI sequence of EMAs and TMI component delivery will begin (see Figure 2).

Figure 2. TMI Sequence

There will be two decision points per day. Decision points will be randomly selected within a 12 hour window starting at the participant's pre-selected start time. There will be at least 4 hours between the two decision points. At each decision point, participants will receive the "decision point EMA." Upon completion of the decision point EMA, participants will be randomized to one of three options: (1) a maternal-focused message (.40 probability); (2) a drinking-focused message (.40 probability); or (3) no message (.20 probability). Fifteen minutes after randomization, participants will receive the "proximal outcome EMA." This sequence will repeat 2 times per day, at each decision point. Participants will also be sent a "morning survey" each morning within 30 minutes of their selected start time that will ask questions about the prior day. After each survey prompt, the survey will be

available for up to 60 minutes, with 2 reminder prompts sent (every 20 minutes). Surveys that are not completed within the 60 minute window will expire.

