Discrimination	
1. At any time yesterday did you feel that you were treated unfairly? (yes/no)
 
2. What was the main reason(s) for the unfair treatment that you experienced yesterday? (check all that apply)
 
 a. Your age b. Your gender c. Your race d. Your ethnicity or nationality e. Your religion f. Your height or weight g. Some other aspect of your appearance h. A physical disability i. Your sexual orientation j. Your drinking k. Your smoking l. Your other substance use m. Being poor n. Being a mother o. Other 
i. For "What was the main reason(s) for the unfair treatment that you experienced yesterday?" you selected other. Please write your response below:
 
3. Who treated you unfairly yesterday? (check all that apply)
 
 a. Family member b. Partner c. Stranger d. Acquaintance e. Employer f. Health care provider g. Other social service provider h. Other _____ 
i. For "Who treated you unfairly yesterday?" you selected other. Please write in your response below:

Decision Point/Daily EMA

[sent 2x daily]

Construct	Items
	
1. Were you with your baby since the last survey you completed? Yes/no [IF NO: Skip Baby Fussiness]
 
2. Will you be with your baby in the next hour? Yes/no [IF NO: Skip Maternal SE]

Maternal SE	How confident are you that you will be able to meet your baby's needs (such as needs to be fed, changed, soothed, or entertained) over the next hour? [Not at all confident to extremely confident 1-7]
Drinking SE ³³	How confident are you that you can avoid drinking for the next hour? [1 = not at all confident to 7 = extremely confident]
Stress ³⁴	Rate your overall stress level right now 1-7, very low to very high.
Mood	
1. What is your overall feeling right now [very unpleasant to very pleasant 1-7]
 
2. What is your overall energy level right now [very low to very high 1-7]
 
3. What is your anxiety level right now [very low to very high 1-7]

Fatigue ¹⁶	
1. How physically exhausted are you right now?
 
2. How mentally exhausted are you right now?
 
[not at all to extremely 1 -7]

Baby Fussiness ³⁵	
1. Since your last assessment, how many times did your baby fuss, cry, or seem upset? [0, 1, 2, 3, 4, 5, 6, 7, 8, 9, 10 or more times]
 
2. How many of these times were you able to successfully soothe your baby? [all of them, most of them, some of them, a few of them, none of them]

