Intent to Drink ³³	How committed are you to not drink in the next hour? [1 = not at all to 7 = extremely]
Urge to Drink	How strong is your urge to drink right now? 1= very low, 7=very high

Drinking	4. Did you consume any alcohol in the past hour? Yes/no 5. If yes, how many drinks did you consume?
----------	--

Proximal Outcome EMA

Construct	Items
Maternal SE	How confident are you that you will be able to meet your baby's needs (such as needs to be fed, changed, soothed, or entertained) over the next hour? [Not at all confident to extremely confident 1-7]
Drinking SE ³³	How confident are you that you can avoid drinking for the next hour? [1 = not at all confident to 7 = extremely confident]
Intent to Drink ³³	How committed are you to not drink in the next hour? [1 = not at all to 7 = extremely]
Urge to Drink	How strong is your urge to drink right now? 1= very low, 7=very high
Drinking	6. Did you consume any alcohol since the last survey you received? Yes/no 7. If yes, how many drinks did you consume?
Stress coping	1. Since the last survey you completed, did you use any strategies to cope with negative feelings or stress? a. I didn't experience negative feelings or stress since the last survey b. I drank alcohol c. I changed my thinking d. I changed my current situation to cope with negative feelings or stress e. I found something else to do f. I sought advice or support g. I came up with a plan to cope with negative feelings or stress h. I set a goal or kept track of my progress towards my goal i. I directly communicated my needs to others j. I tried to relax k. I took medication l. I pushed negative feelings or stress away m. I used another strategy n. I didn't use any strategies to cope with negative feelings or stress 2. In the previous question you indicated that you took medication to cope with negative feelings or stress. Was this medication intended for the purpose of managing negative feelings or stress/for the purpose of managing alcohol cravings? a. Yes b. No 3. Was this medication prescribed to you by your healthcare provider? a. Yes b. no 8. You selected "I used another strategy to cope with stress". Please describe what you did below:

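### Maternal self-efficacy is skipped before randomization when the woman will be away from her baby, but the post-randomization item and its analysis carry no matching restriction

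*Combined protocol and SAP*

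**What the plan says.** The Decision Point/Daily EMA table opens with a with-baby question that controls whether maternal self-efficacy is asked: "Will you be with your baby in the next hour? Yes/no [IF NO: Skip Maternal SE".

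The Proximal Outcome EMA table begins with the same item on the same 1–7 scale: "How confident are you that you will be able to meet your baby's needs (such as needs to be fed, changed, soothed, or entertained". It prints no with-baby question, no skip and no not-applicable response for this item.

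TMI Sequence and Randomization fixes the order: "Upon completion of the decision point EMA, participants will be randomized to one of three options". The with-baby answer is therefore a pre-randomization variable. The proximal survey goes out 15 minutes later, and each survey stays open for up to 60 minutes.

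MRT Data Analysis starts from a multilevel model with an intercept and a component term. It reads the coefficient as a mean difference between occasions with and without the component, averaged over the study. No section restricts this for maternal self-efficacy, and none confines maternal-focused messages to times with the baby. Self-efficacy is one of three named proximal outcomes. Sample and Power says that results will be interpreted by effect size and will inform a later, fully powered trial.

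**The concern.** The two surveys treat the same item differently. Before randomization, confidence in meeting the baby's needs over the coming hour is not asked of a woman who will be away from the baby. After randomization, nothing printed stops the item from being put to her. Her answer would then be hypothetical, and a maternal-focused message has less scope to move it.

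Maternal self-efficacy is the only parenting-specific item in the proximal survey, so it bears directly on the comparison of maternal-focused with drinking-focused messages. Pooling applicable and inapplicable occasions would make maternal-focused messages look weaker on this item than they are when the woman is with her baby, and that smaller effect size would be carried into planning of the next trial.

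**Working it through.** The documents give no power or sample-size calculation, so there is no stated figure to reproduce. The check is a comparison of the two survey tables plus an illustration of size.

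**Inputs from the documents.** 50 women (Sample and Power); two decision points a day for 28 days; allocation probabilities 0.40 maternal, 0.40 drinking and 0.20 no message (TMI Sequence and Randomization).

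**Input not in the documents.** q, the share of decision points answered 'no' to the with-baby question. It is assumed here to lie between 5% and 40%.

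**1. Counts.** Scheduled decision points: 50 × 28 × 2 = 2,800. Expected split: 2,800 × 0.40 = 1,120 maternal, 1,120 drinking, and 2,800 × 0.20 = 560 no message. This assumes that every prompt is completed and leaves out the optional nighttime sequence. Decision points answered 'no' number 2,800 × q.

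| q | Decision points answered 'no' | Pooled effect as a multiple of the effect at applicable times, (1 − q) |
|---|---|---|
| 5% | 140 | 0.95 |
| 10% | 280 | 0.90 |
| 20% | 560 | 0.80 |
| 30% | 840 | 0.70 |
| 40% | 1,120 | 0.60 |

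**2. Balance.** At q = 10% the 280 'no' occasions are expected to split 112, 112 and 56, which is 10% of each option. The answer precedes randomization, so there is no bias between options.

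**3. Dilution.** Let Δ be the effect at 'yes' occasions and δ the effect at 'no' occasions. The pooled effect is (1 − q)Δ + qδ. With δ near zero this is (1 − q)Δ, the last column above. If δ were half of Δ, the multiple at q = 20% would be 0.80 + 0.20 × 0.5 = 0.90.

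**4. Efficiency of restricting.** With equal variance and δ = 0, squared effect over variance is proportional to n(1 − q)² for the pooled analysis and n(1 − q) for the restricted one, which loses a share q of the data. The gain is 1/(1 − q): 1/0.9 = 1.11 at 10% and 1/0.8 = 1.25 at 20%.

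**5. Simulation check.** 400 runs per setting; 2,800 independent normal outcomes with SD 1; effect 0.30 at 'yes' occasions and zero at 'no' occasions; maternal message against no message.
- The all-occasions estimate averaged 0.270, 0.235 and 0.210 at q = 10%, 20% and 30%. The formula gives 0.27, 0.24 and 0.21.
- The restricted estimate averaged 0.295 to 0.302 over all settings.
- When answers at 'no' occasions were set 1.5 SD lower, the SD of the all-occasions estimate at q = 20% was 0.063, against 0.055 without the shift. The restricted estimate had 0.059 in both cases. This is the added noise.

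The simulation ignores correlation within women. It checks the formulas, not the precision that this trial will reach.

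**6. Overlap of the two hours.** The first hour runs from about 0 to 60 minutes after randomization. The proximal survey can be answered from 15 to about 75 minutes after. The overlap is therefore at most 60 − 15 = 45 minutes, and none if the survey is answered after 60 minutes.

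**The case against.** The strongest objection is that the proximal survey table is not a full branching specification. Its follow-up items on medication and on other strategies are plainly conditional, yet no condition is printed. A reader might infer that the app puts the maternal item to every woman after randomization; the documents do not establish that. If the app carries the skip forward, there is no dilution. This stands, and it limits the point to the plan as printed. It does not remove the point: in that case the outcome is missing by design on those occasions, and the plan should say so.

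Other stronger readings also fail:
- **Bias between options.** Not supported, since the with-baby answer comes before randomization.
- **No effect is possible when the baby is absent.** Too strong. The later hour is shifted, so some women may be back with the baby, and general confidence could change.
- **1.23 or 1.56 times the data are needed.** These are 1/0.9² and 1/0.8², measured against a trial in which every decision point is applicable. The fix discards data, so the net gain is 1.11 or 1.25. There is also no power target to miss.
- **The missing pre-randomization value damages the analysis.** The one model described has no such term. Only a change-score or adjusted model would lose these occasions.
- **This is the key outcome for maternal messages.** The documents do not rank the proximal outcomes.

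It is also fair to say that q may be small: eligibility requires a birth within the past four weeks and an infant who stays in the mother's care. And an average over all occasions is a legitimate estimand if it is chosen deliberately.

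**Conclusion.** The point holds as a minor but real inconsistency. The plan treats maternal self-efficacy as not applicable when the woman will be away from her baby, then prints the item without that restriction after randomization and averages over every occasion. The consequence is an attenuated and noisier effect size for this one outcome; the randomized comparison remains valid.

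The attenuation is to about 0.90 of the effect at applicable times if 10% of decision points are answered 'no', and 0.80 if 20% are. Restricting the analysis would improve efficiency by about 1.11 and 1.25. These figures rest on an assumed q, little or no effect at 'no' occasions, and (for efficiency) similar outcome variance at both kinds of occasion. They apply only if the app does ask the item at those times. Feasibility, the primary goal of the pilot, is not threatened.

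**What to change.** 1. Define the main maternal self-efficacy analysis on decision points answered 'yes' to the with-baby question in the decision point survey. Keep the all-occasions analysis as a sensitivity analysis.
2. State whether the app carries the skip into the proximal survey. If it does, record the outcome as missing by design at those decision points.
3. Prefer the analysis filter to a hard skip in the app, so that valid answers from women who rejoin the baby by the later survey are not lost.
4. Do not select occasions by whether the woman is with her baby after randomization, because a message could influence that.
5. Report the observed share of 'no' answers, which replaces the assumed q and shows whether the issue matters for the next trial.

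The cost is one filter on data already collected and a few sentences in MRT Data Analysis. The downside is slightly fewer decision points for this outcome, and an estimand limited to times when the woman expects to be with her baby.

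### The drinking item in the Proximal Outcome EMA looks back to the last survey received, so its window takes in 0 to 60 minutes before randomization; the cost is noise and a smaller standardized effect, not confounding

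*Combined protocol and SAP*

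**What the plan says.** Under TMI Sequence and Randomization, each decision point starts with a prompt for the decision point EMA. Two reminders follow at 20-minute intervals, and "Surveys that are not completed within the 60 minute window will expire". The random draw comes later than the prompt: "Upon completion of the decision point EMA, participants will be randomized to one of three options". The proximal outcome EMA is sent 15 minutes after the draw.

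Three items bear on the look-back:

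- Decision Point/Daily EMA, drinking: "Did you consume any alcohol in the past hour".
- Proximal Outcome EMA, drinking: "Did you consume any alcohol since the last survey you received", followed by a drink count.
- Proximal Outcome EMA, stress coping: "Since the last survey you completed, did you use any strategies to cope with negative feelings or stress". The drink-coping item uses the same anchor.

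Alcohol use is named as the distal outcome; the proximal outcomes are motivation, self-efficacy and self-regulation (Study Purpose and Aims; Purpose of Pilot MRT). The morning survey has its own item on drinking the day before. Sample and Power says that results will be read by effect size, not significance. MRT Data Analysis starts from models with a constant and the component term only, defines the coefficient as a mean difference, and adds a standardized effect size.

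**The concern.** Received and completed are different moments, and only completion coincides with randomization. Take a woman prompted at 5:00 who has a drink at 5:10, completes the survey at 5:40, is randomized, and is sent the proximal survey at 5:55. On the literal wording, the 5:10 drink belongs in her answer to the proximal item, although the message came later. The same drink also falls within the hour asked about at 5:40. The coping items one screen away would leave 5:10 out, so two parts of one survey cover different periods, and the plan gives no reason.

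This is the only direct drinking question, and the only drink count, tied to a single randomization; the morning item sums over a whole day with two daytime decision points. Drinks taken before the message carry no information about it. In a pilot that reads its results by effect size, extra noise in this item makes a message look weaker than it is on a standardized scale.

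**Working it through.** The plan states no power or effect figure to reproduce, so the check is one of timing.

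**Inputs (TMI Sequence and Randomization).** L = minutes from decision point prompt to completion, 0 to 60. D = minutes from proximal prompt to answer, 0 to 60. Fixed gap between randomization and proximal prompt = 15 minutes.

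**Windows.** As written: L + 15 + D, that is 15 to 135 minutes, of which L precede randomization. Anchored to completion: 15 + D, that is 15 to 75 minutes, with none before randomization. The pre-randomization share is L/(L + 15 + D).

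**Effect on each scale.** Assume, for illustration only, a constant Poisson drinking rate r and a message that multiplies later drinking by 0.5.

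- Mean difference in counts: r(L + 15 + D) − r(L + 0.5(15 + D)) = 0.5r(15 + D). L cancels.
- Standardized effect, taking the SD as that of the count itself: the SD grows from √(r(15 + D)) to √(r(L + 15 + D)), so the effect is multiplied by √((15 + D)/(L + 15 + D)).
- Ratio of counts: (L + 0.5(15 + D))/(L + 15 + D).

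| L | D | Window (min) | Share before randomization | Multiplier of standardized effect | Observed ratio (true 0.50) |
|---|---|---|---|---|---|
| 0 | 0 | 15 | 0% | 1.00 | 0.50 |
| 5 | 0 | 20 | 25% | 0.87 | 0.63 |
| 20 | 0 | 35 | 57% | 0.65 | 0.79 |
| 40 | 0 | 55 | 73% | 0.52 | 0.86 |
| 60 | 0 | 75 | 80% | 0.45 | 0.90 |
| 5 | 60 | 80 | 6% | 0.97 | 0.53 |
| 20 | 60 | 95 | 21% | 0.89 | 0.61 |
| 60 | 60 | 135 | 44% | 0.75 | 0.72 |

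- Yes/no difference: multiplied by exp(−rL), because a woman who drank in the gap is a 'yes' whatever she is sent. With an assumed r of 0.05 drinks per 15 minutes, this is exp(−0.067) = 0.94 at L = 20 and exp(−0.2) = 0.82 at L = 60. With D = 0, the absolute difference goes from 0.0241 to 0.0225 and 0.0197. At lower rates the factor is closer to 1.

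**Double reporting.** The past-hour item is answered at about the time of completion. Since L is at most 60, the gap lies inside that hour, so a gap drink can appear in both records. Subtracting one item from the other does not repair this: the past hour also reaches 60 − L minutes back before the prompt (40 minutes when L = 20).

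**Other sequences.** The 60-minute bound holds only where a prompt is sent. The optional nighttime sequence has none, so the last survey received may be much earlier, or undefined. The morning survey goes out within 30 minutes of the start time, when the decision window also opens. If it arrives between the two prompts, it becomes the last survey received and shortens the window.

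**The case against.** The strongest reply is that little in the plan rests on this item. Drinking is the distal outcome, with its own morning measure; the main-effect models are specified for the proximal outcomes, among which drinking is not named; and the primary goal is feasibility. No section says that the two drinking items will be compared or summed. All of that stands, and it limits the weight of the point.

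Three stronger readings are tempting, and the documents do not support them:

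- *The comparison of messages is biased.* L and any gap drinks are fixed before the draw, so they are balanced in expectation and cancel from a mean difference in counts.
- *The effect shrinks by the same share as the window.* That holds for a relative change under a constant rate. The plan uses a mean difference and a standardized effect. At L = 20 and D = 0 the share is 57%, so shrinkage by the share would leave 0.43 of the effect; the standardized multiplier is 0.65.
- *This is the only drinking measure tied to a randomization.* The stress-coping list includes drinking alcohol as a response and already looks back to completion, though it captures only drinking to cope.

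Two further points are fair. Prompt answers make the problem small, and no delay distribution is given. A woman may also take a reminder as the survey she received: in the 5:00 example the second reminder falls at 5:40, when she completes it. That makes the item ambiguous rather than certain to mislead, but an item whose starting point depends on the reader still needs fixing.

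**Conclusion.** The point holds as a wording fault in one secondary item. In prompted sequences the look-back includes 0 to 60 minutes before randomization, 0% to 80% of the window, and a drink in that gap can be recorded twice. These figures follow from the timing rules alone.

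The consequence is lost precision: more noise, a standardized effect multiplied by something between 0.45 and 1.00, a ratio pulled towards 1, and some attenuation of the yes/no difference. Those sizes rest on a constant Poisson rate, an assumed halving of drinking for the ratio, and an assumed rate for the yes/no item. Drinking that clusters in episodes or varies between women would change them. A reader might infer that the pilot's daily drinking results, or its results on motivation, self-efficacy and self-regulation, are compromised. They are not, since those items do not use this look-back. The change is still worth making, because a pilot is meant to settle its instruments before the powered trial and the correction costs almost nothing.

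**What to change.** Anchor the drinking item in the Proximal Outcome EMA to randomization by having the app insert the clock time at which the decision point EMA was completed, for example *since 5:40 PM*. If the app cannot do this, word it *since you completed the survey just before this one in this sequence*. The shorter *since you completed the last survey* is not enough: a morning survey completed between the draw and the proximal EMA would move the start past randomization and drop post-message time. Use the same anchor in the nighttime sequence, and keep the prompt and completion times of every survey.

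The cost is one item in the app and the matching protocol text, with no added burden for participants. If enrolment has begun, flag the item version in the data. For answers already collected, response delay and past-hour drinking both precede randomization, so either can be used as a covariate or to define a subset without breaking the comparison. In prompted sequences, a 'no' to past-hour drinking also rules out, by her own report, a drink between the prompt and that answer.

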Drink Coping	1. Since the last survey you completed, did you use any strategies to manage the urge to drink alcohol? a. I didn't experience an urge to drink alcohol since the last survey b. I changed my thinking c. I changed my current situation to cope with negative feelings or stress d. I found something else to do e. I sought advice or support f. I came up with a plan to cope with negative feelings or stress g. I set a goal or kept track of my progress towards my goal h. I directly communicated my needs to others i. I tried to relax j. I made an effort to stay safe and avoid risks while drinking alcohol k. I took medication l. I pushed negative feelings or stress away m. I used another strategy n. I didn't use any strategies to cope with negative feelings or stress 2. In the previous question you indicated that you took medication to cope with the urge to drink alcohol. Was this medication intended for the purpose of managing negative feelings or stress/for the purpose of managing alcohol cravings? a. Yes

	
b. No
 
3. Was this medication prescribed to you by your healthcare provider?
 
a. Yes
 
b. No

--	--

You selected "I used another strategy to cope with the urge to drink alcohol". Please describe what you did below:

MRT Data Analysis

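### In the printed Drink Coping item, the only answer for using no strategy refers to stress, not to the urge to drink: a minor wording error

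*Combined protocol and SAP*

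**What the plan says.** The Combined protocol and SAP prints two coping items in the Proximal Outcome EMA table under MRT Measures. The section TMI Sequence and Randomization places that survey after each randomization: "Fifteen minutes after randomization, participants will receive the" proximal outcome EMA. The items are therefore part of live data collection.

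The Stress coping item asks about strategies for negative feelings or stress. Its option a covers the woman who had none: "a. I didn't experience negative feelings or stress since the last survey". Its option n denies using any strategy and fits its stem.

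The Drink Coping item asks "did you use any strategies to manage the urge to drink alcohol". Option a covers the woman who had no urge, and b to m are strategies. The only option that denies using a strategy is "n. I didn't use any strategies to cope with negative feelings or stress".

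No section says how n is to be read or scored. No section says whether the coping items accept one answer or several; the Discrimination items in the morning survey do print such a rule.

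**The concern.** The stem and its negative answer name different targets. The natural contrast to using a strategy against an urge is having an urge and using none, and no printed option says that in its own words. This is the only item in the Proximal Outcome EMA that asks about strategies for managing an urge. Any later summary of urge coping from the pilot would therefore rest on an answer whose meaning depends on how each woman read it.

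What is at stake is the secondary goal, the proof-of-concept data on proximal outcomes. The primary goal is feasibility and acceptability, and it does not use the content of this answer.

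**Working it through.** No arithmetic applies and the plan gives no figure to reproduce. The check sets the two printed items side by side.

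| Part | Stress coping | Drink Coping |
|---|---|---|
| Stem | Stress or negative feelings | Urge to drink |
| Option a | No stress occurred | No urge occurred (adapted) |
| Staying safe while drinking | Not listed | Option j (added) |
| Changing the situation | Option d, stress wording | Option c, same text |
| Making a plan | Option g, stress wording | Option f, same text |
| Pushing feelings away | Option l, stress wording | Option l, same text |
| No strategy used | Option n, stress wording | Option n, same text |

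Each item has 14 options, and 12 texts appear in both lists. Under the Drink Coping stem, four options carry stress wording: c, f, l and n.

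**Carry-over or choice.** Where Drink Coping was adapted, it names the urge or drinking: option a, option j, the opening of the medication follow-up, and the prompt after option m. Option n was not adapted. Other slips suggest a working template. Both medication follow-ups ask "Was this medication intended for the purpose of managing negative feelings or stress/for the purpose of managing alcohol cravings", with the two purposes merged. The prompts after option m quote "I used another strategy to cope with stress" and "I used another strategy to cope with the urge to drink alcohol", although option m has neither ending in either list.

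**What n means under each reading, for a woman who had an urge.**

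| Situation | n read literally | n read under the stem |
|---|---|---|
| Urge not managed, stress coped with | False | True |
| Urge not managed, no stress or stress not coped with | True | True |
| Urge managed, no stress or stress not coped with | True | False |
| Urge managed, stress coped with | False | False |

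The readings part in the first and third rows. In the first, a literal reader finds no option that describes her. In the third, n is literally true although she managed the urge, but she also has b to m to choose from.

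**The same standard for c, f and l.** If the stem governs, c, f and l are urge strategies and n means no urge strategy, so the item works. If the literal text governs, a woman who coped only with stress could tick c, f or l truthfully, so those ticks do not prove a managed urge either. One standard has to cover all four options, and the printed plan does not say which.

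**The case against.** The strongest reply is that the stem sets the topic. A woman who has just been asked about her urge will mostly take n to mean that she did nothing about it. For n alone to hide a managed urge, she would have to pass over every strategy from b to m, including the catch-all m, and choose a statement about stress instead. MRT Data Analysis names no coping score and no endpoint built on n. The deployed survey may already differ from the table. All of this stands, and it is why the point is minor and why n is called ambiguous rather than wrong.

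It does not remove the point. The stem reading is likely but not secured by the text, nothing in the plan adopts it, and the correction costs almost nothing.

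A reader might go further in four ways that the documents do not support:

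- That the self-regulation outcome is misclassified. Self-regulation is named as a proximal outcome, but no section says which items measure it.
- That the comparison of maternal-focused and drinking-focused messages is biased. Nothing shows that n is read differently by message type.
- That the size can be taken from the number of scheduled surveys or from a count of answer patterns. No urge rate is given, the patterns are not equally likely, and the optional nighttime sequence is not itemised, so even the maximum number of administrations is not fixed.
- That n given beside a reported stress strategy must have been read under the stem. An inconsistent pair can also be a careless or mistaken answer.

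**Conclusion.** The printed Drink Coping item contains a wording error: its only answer for using no strategy is about stress, while the stem is about the urge to drink. As printed, n is ambiguous. Severity is minor.

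The size of any misclassification is unknown and cannot be derived from the documents. The conclusion about the printed text rests on direct comparison and is firm. Whether any data are affected rests on two assumptions that the documents cannot settle: that the deployed survey matches the table, and that some women read n literally.

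**What to change.** 1. Check the wording of the coping items in the deployed survey, and whether they accept several answers.
2. If n matches the table, reword it to: *I didn't use any strategies to manage the urge to drink alcohol*. Align c, f and l with the urge stem at the same time. If this happens mid-trial, put a version flag on each record.
3. For data already collected under the old wording:
   - In the main summary, read n under the stem, as no urge strategy.
   - Flag records where n is the only answer. As a sensitivity check, count those records as urge managed as well. The two results bound the effect of the ambiguity in n.
   - Treat n ticked together with a, or with any of b to m, as an inconsistent response and report how many there are. If only one answer is allowed, this case cannot arise.

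The bound covers n only. It does not recover a stress strategy recorded under c, f or l by a literal reader, which is why those three should be aligned in the same edit.

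The cost is one check of the live survey, up to four text strings, a minor amendment, and a version flag if the change falls mid-trial. The rule for existing data needs no new data.
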